1.4.2 Mechanism of Action

Lapatinib has been shown to be a potent and selective dual inhibitor of EGFR and ErbB2 tyrosine kinase activity with IC50 values of 10.2 and 9.8 nM, respectively (Rusnak 2001). Lapatinib has demonstrated selective growth inhibition of human cell lines (head and neck, breast, and gastric) in vitro (IC90 values <2.26 µM or 1313 ng/mL) with no outgrowth observed up to 18 days following cessation of treatment. Growth inhibition corresponded with the ability of lapatinib to inhibit phosphorylation of Akt. These studies suggested that inhibition of EGFR by lapatinib resulted preferentially in cell growth arrest, while inhibition of ErbB2 led to cell growth arrest and apoptosis after 72 hours. Treatment with lapatinib leads to arrest of tumor cell growth and/or apoptosis, even in the presence of saturating concentrations of epidermal growth factor (EGF). Treatment of tumor xenografts resulted in inhibition of activation of EGFR, erbB2, Erk1/2, and Akt (Xia 2002).

1.4.3 Antitumor Activity

The ability of lapatinib to inhibit the growth of EGFR-over-expressing cell lines (IC50 <0.16 µM) was observed to be equal to that of other EGFR inhibitors being tested in clinical trials (e.g. gefitinib/Iressa™ or erlotinib/Tarceva™). With the exception of ErbB4, lapatinib was >300-fold more selective towards ErbB2 and EGFR kinase inhibition than to other kinases tested. Lapatinib demonstrated potent growth inhibition of human breast ductal (BT474) and head and neck (HN5) tumor xenografts in mice. A dose response inhibition was observed in both models receiving lapatinib (30 or 100 mg/kg twice daily orally for 21 days). Complete inhibition of tumor growth was seen in mice receiving 100 mg/kg (Rusnak 2001).

1.4.4 Signal Transduction

Lapatinib has been shown to inhibit Erk1/2 and Akt phosphorylation (pErk and pAkt) in both EGFR and erbB2-expressing cell lines (BT474 and HN5). The ability of lapatinib to inhibit pAkt was associated with a 23-fold increase in the percentage of cells undergoing apoptosis compared to control cells. Similarly, lapatinib treatment of BT474 and HN5 xenografts in mice also resulted in inhibition of Erk1/2 and Akt phosphorylation. These results suggested that lapatinib treatment of EGFR/erbB2 expressing tumors could lead to inhibition of downstream signaling events (Xia 2002).

A study of human breast cancer cell lines that over-express EGFR or erbB2 (SUM102, SUM149, SUM185, and SUM225) reported that treatment with lapatinib resulted in inhibition of cell proliferation that was associated with inhibition of Erk phosphorylation. Inhibition of Erk phosphorylation also correlated with radiosensitization of cell lines pretreated with lapatinib (Zhou 2003).

1.4.5 Toxicology

A range of toxicology studies has been conducted to support the oral administration of lapatinib to humans. Repeat oral dose toxicity studies have been completed in rats and dogs for up to 6 and 9 months, respectively. The effects of lapatinib on fertility in the rat and embryofetal development in the rat and rabbit have been investigated. A range of genetic toxicity studies has been performed in vitro and in vivo. The significant findings from the toxicology studies are summarized below.

- Following single oral administration, lapatinib was well-tolerated by both CD-1 mice and Wistar Han rats at doses up to 2000 mg/kg. Treatment-related findings consisted of reversible changes in body weight and body weight gain as well as reversible GI effects.
- A 13-week oral dose ranging pilot carcinogenicity study in mice showed that treatment with lapatinib at doses up to 200 mg/kg/day was generally well tolerated. Microscopic changes attributable to treatment with lapatinib were noted in the liver and preputial gland of males and large intestines (cecum and colon) of males and females.
- Administration of lapatinib to rats and dogs for up to 6 months or 9 months resulted primarily in exaggerated pharmacologic effects and organ toxicities generally associated with degenerative and/or inflammatory epithelial changes (GI tract and accessory digestive organs, skin, mammary gland, liver and prostate). Other treatment-related effects included clinical signs, decreased body weight and food consumption, organ weight changes and alterations in clinical pathology parameters. Following the recovery period, treatment-related changes were either significantly improved or completely reversed.
- There were no effects on male or female rat gonadal function, mating, fertility or pregnancy nor were there any increases in the number or incidence of any malformations when rats or rabbits were given lapatinib during the period of major organogenesis. At maternally toxic doses (≥ 60 mg/kg/day in rats and rabbits), lapatinib treatment was associated with growth retardation and developmental variations.
- In genetic toxicity studies, lapatinib was demonstrated to be non-mutagenic and non-clastogenic.

1.5 Quality of Life and Patient-Reported Outcomes

This study affords another unique opportunity: to prospectively explore quality of life (QOL) and patient-reported outcomes (PROs) in this disease. Most curative intent, multimodality treatment regimens in locally advanced head and neck cancer are associated with significant acute and late toxicities. Standard validated QOL measurements used in patients treated for squamous cell

carcinomas of the head and neck have demonstrated that a considerable proportion of patients report debilitating functional compromise and psychosocial morbidity (Bjordal 2000; Weymuller 2000; Ringash 2005; Martino 2008; Logemann 2008). There also is a growing body of literature supporting a relationship between better QOL with superior treatment outcomes (Siddiqui 2008; Karvonen-Gutierrez 2008). To our knowledge, data of this nature is nonexistent among patients treated with lapatinib with chemoradiation for non-HPV locally advanced head and neck cancer, and this trial would be an ideal mechanism to collect and analyze this subjective, patient-reported longitudinal data. Therefore, we will explore the impact of treatment assignment on QOL/PROs after initial therapy and during maintenance therapy using validated instruments: the Functional Assessment of Cancer Therapy (FACT) H&N subscale (12 items); the 15-item University of Michigan Xerostomia-Related Quality of Life Scale (XeQOLS) and the Performance Status Scale for Head and Neck Cancer (PSS-HN) [Ringash 2007; Ringash 2008; Murphy 2007; Henson 2001; Rodgers 2009; List 1996; 1999]. These outcomes will be assessed at baseline (pretreatment) and at 3, 12, and 24 months from completion of radiation treatment.

In this phase II trial, preliminary data will be obtained for assessing the extent to which quality of life, swallowing, and xerostomia are adversely affected by the addition of lapatinib in this setting. It is hypothesized that the above indicators, as measured by the FACT-H&N subscale, PSS-HN, and XeQOLS instruments, will be less favorable for patients undergoing chemoradiation with lapatinib relative to chemoradiation and placebo, at 3 months after completion of radiation treatment. The current investigation is exploratory, but allows us to explore the relative importance of these QOL/PROs in this setting. The goal of including an exploratory QOL/PROs correlative component is to generate estimates of effect sizes (means, standard deviations) that will guide the statistical power and effect size estimates for a subsequent phase III trial.

1.5.1 QOL and PRO Assessments

1.5.1.1 The FACT-HN is a multidimensional, patient self-report QOL instrument specifically designed and validated for use with head and neck cancer patients. The FACT-HN module consists of a 12-item head and neck subscale targeting head and neck related symptoms and side effects (Cella 2000; Ringash 2004; Ringash 2005; Ringash 2007; Ringash 2008), and can be administered independently from the general FACT-G instrument. High scores indicate better QOL and functioning. This tool takes approximately 5-10 minutes to complete.

1.5.1.2 The PSS-HN is a clinician/interviewer administered assessment that focuses on three functional areas: Normalcy of Diet, Eating in Public, and Understandability of Speech. The score on each of the three subscales ranges from 0-100, with higher scores indicating better performance (List 1996; List 1999; List 2000).

1.5.1.3 The XeQOLS instrument is patient self-report measure that consists of 15 items on a 5-point Likert-type scale covering mouth/throat dryness and its impact on four major domains of oral health-related quality of life: physical functioning, personal/psychological functioning, social functioning, and pain/discomfort issues [Murphy 2007; Henson 2001; Rodgers 2009]. The XeQOLS takes the patient approximately 5 minutes to complete.

1.6 Correlative Studies

While the importance of EGFR in HNSCC has been well established, a direct role of HER2 in tumorigenesis and treatment resistance of HNSCC is not clear and is poorly understood. HER2 is expressed in the range of 0-47% in HNSCC depending on the antibodies used, staining conditions and scoring systems of immunohistochemistry (IHC). Hou, et al. have shown that HER2 expression progressively increased as oral disease progresses from normal mucosa, pre-malignant lesions to invasive oral SCC; however, its association with tumor stage, locoregional control, and survival as a prognostic marker varies depending on the sample size and evaluation methods. In a recent study by Cavalot, et al., a high membranous HER2 protein expression was an independent prognostic factor for disease-free survival. To date, HER2 expression has never been evaluated as a predictive biomarker of HER2-specific inhibitor therapy in HNSCC. Biologic correlative studies of the TryHard study will address these important scientific questions as permitted by the study design that includes a randomized control arm.

Dual-targeting of EGFR and HER2 also provides a strong rationale for the use of lapatinib with chemoRT for LA-HNSCC. There is evidence that heterodimers containing HER2 as a partner is the most potent combination for the receptor activity compared to other dimers formed by 4 family

members of HER receptors. Inhibitory effects of 1 receptor have shown to be negated by heterodimers formed by the rest of uninhibited HER receptor family members. The extent of EGFR-HER2 and HER2- HER3 heterodimerization in HNSCC is not known; however, potentially heterodimerization may occur and contribute to resistance given EGFR-specific tyrosine kinase inhibitors. Therefore, a dual inhibition using lapatinib warrants further investigation and will be examined in the correlative studies.

1.6.1 HER2 Expression as a Predictive Biomarker of Lapatinib Response

Since lapatinib is a dual inhibitor of both EGFR and HER2, it is logical to evaluate HER2 protein expression and gene amplification in addition to the EGFR analysis and HPV assay (for oropharynx only). For this aim, we propose the following:

- HER2 protein expression determined by image-guided quantification of IHC staining (Cavalot 2007);
- HER2 gene amplification determined by FISH (Khan 2002).

1.6.2 EGFR-HER2 Heterodimer Expression as a Predictive Biomarker of Lapatinib Response

Activation of EGFR involves either homodimerization or heterodimerization between EGFR and HER2. The in situ proximity ligation assay (PLA) was developed to enable detection of individual proteins and protein-protein interactions in cell lines and tissues, specifically paraffin embedded tissues (Söderberg 2006; Weibrecht 2010). The approach uses oligonucleotides attached to the antibodies against the 2 target proteins, in this case, pEGFR and pHer2. The oligonucleotides on the proximity probes when brought into close proximity by protein dimerization, serve as templates for the circularization, which can then be amplified and visualized as bright fluorescent RCPs or colometric RCP dots (depending on the type of detection). Since each detected protein dimerization gives rise to one RCP, the detected complexes can be easily enumerated and counted. Tissue PLA has been used to assay for HER-family dimerization in tissue samples using the Duolink Kit from Olink Bioscience (Uppsala, Sweden). We have also evaluated pEGFR dimerization in head and neck squamous cell carcinoma and found that this approach can be readily applied to tissue microarray of formalin-fixed, paraffin-embedded tumor tissues. We propose to use this assay to evaluate EGFR homodimerization and EGFR-HER2 heterodimerization on pretreatment tumor samples as a potential predictor for lapatinib efficacy.

1.6.3 EGFR Ligand Expression Levels in Tissue and Blood as a Predictive Biomarker of Lapatinib Response

mRNA expression of EGFR ligands such as TGFA, AREG, EREG, and HB-EGF have been shown to correlate with prognosis in HNSCC (Grandis 1998) and predict for efficacy of EGFR targeting, specifically cetuximab in colorectal cancer (Khambata-Ford 2007; Hatakeyama 2010). Based on this information, we propose to evaluate the following EGFR ligand expression levels as a biomarker predictor of lapatinib response: TGFA, AREG, EREG and HB-EGF mRNA levels determined by RT-PCR (Grandis 1998; Khambata-Ford 2007; Hatakeyama 2010). In addition, we will measure HB-EGF (one of the EGFR ligands) protein levels in plasma samples collected at pre-, end-of-radiation, and post-treatment (Hatakeyama 2010).

1.6.4 Variant EGFR 497 Arg Allele and EGFR Intron 1<20 CA Repeats as a Prognostic Biomarker of Poor Relapse-Free Survival and a Predictive Biomarker of Lapatinib Sensitivity

Variant EGFR 497 Arg allele and EGFR intron 1<20 CA repeats have been shown to be a prognostic biomarker of poor relapse-free survival (RFS) in HNSCC. However, its role in predicting lapatinib sensitivity is unknown in these patients. Since these polymorphisms can be readily measured from circulating WBC, we propose to evaluate these allelic variants in patients enrolled on this study, both to validate their prognostic significance as well as to determine their predictive effect of lapatinib response. The following assays will be performed:

- Assess EGFR gene polymorphism 497 arginine-to-lysine determined by PCR-RFLP using germline DNA collected from pre-treatment PBMC (Zhang 2005);
- Assess EGFR intron 1 CA repeat polymorphisms determined by PCR-RFLP using germline DNA collected from pre-treatment PBMC (Amador 2004).

1.6.5 Validation of Lysyl Oxidase (LOX) and Gli Family Zinc Finger (Gli1) as Biomarkers of Distant Metastasis

We have previously identified LOX and Gli1 as biomarkers for distant metastasis in HNSCC treated with radiation alone on RTOG 90-03 (Le 2009, Chung 2010). The role of these markers in HPV negative patients treated with chemoradiation has not been evaluated. We propose to validate the role of these biomarkers as predictors for distant metastasis by quantifying the level

of these proteins in pre-treatment tumor samples (as previously described in Le 2009 and Chung 2010).

1.6.6 Epithelial-to-Mesenchymal Transition (EMT) as a Prognostic Biomarker of Poor RFS and a Predictive Biomarker of Lapatinib Resistance

EMT is a well known process governing invasion and metastasis in epithelial cell tumors. Although several biomarkers have been suggested to reflect the EMT process, one common hallmark of EMT is increased vimentin expression in the tumor (Frederick 2007). Recently, certain microRNAs, including miR-212, miR-103 and miR-200 have been linked to the EMT process, and their expression levels have been correlated with poor outcomes (Hatakeyama 2010; Martello 2010). In this exploratory study, we proposed to measure EMT by the following 2 approaches and determine whether the levels of these EMT biomarkers correlate with poor RFS and/or lapatinib resistance in the treated patient population.

- Vimentin expression in pre-treatment tumors determined by automated quantitative analysis (AQUA) (Frederick 2007);
- miR-212, miR-103 and miR-200 expression in serum/plasma samples collected at pre-, end-of-radiation, and post-treatment (Hatakeyama 2010; Martello 2010).

2.0 OBJECTIVES

2.1 Primary Objective

2.1.1 To evaluate if the addition of lapatinib to concurrent cisplatin and radiation in this patient population sufficiently improves progression-free survival (PFS) to warrant a phase III trial

2.2 Secondary Objectives

2.2.1 To evaluate if the addition of lapatinib to concurrent cisplatin and radiation in this patient population improves overall survival (OS);

2.2.2 To evaluate if the addition of lapatinib to concurrent cisplatin and radiation in this patient population improves control of distant metastasis;

2.2.3 To evaluate toxicity and tolerability between treatment arms;

2.2.4 To evaluate if the addition of lapatinib to concurrent cisplatin and radiation in this patient population improves local regional control;

2.2.5 To investigate quality of life and patient-reported outcomes between treatment arms;

2.2.6 To explore HER2 expression, amplification and heterodimerization, EGFR ligand expression, EGFR polymorphisms, hypoxia, and EMT characteristics as biomarkers of lapatinib response, sensitivity, and resistance, PFS, and metastasis.

3.0 PATIENT SELECTION (10/3/13)

For questions concerning eligibility, contact the study Data Managers (see the title pages for contact information).

3.1 Conditions for Patient Eligibility (9/27/16)

3.1.1 Pathologically (histologically or cytologically) proven diagnosis (from primary lesion and/or lymph nodes) diagnosis of squamous cell carcinoma of the oropharynx, hypopharynx, or larynx;

3.1.2 For patients with an oropharynx primary, the tumor must be negative for p16 by immunohistochemistry;

3.1.3 Selected stage III or IV disease: patients with T2 N2-3 M0, T3-4 any N M0 are eligible; in addition, p16 negative oropharynx cancer T1 N2b, N2c, or N3; and hypopharynx cancer patients with T1-2 any N+ are eligible, including no distant metastases, based upon the following minimum diagnostic workup:

3.1.3.1 History/physical examination within 28 calendar days prior to registration, including an examination by a Medical Oncologist and Radiation Oncologist and documentation of the patient's weight;

3.1.3.2 Examination by an ENT or Head & Neck Surgeon, including laryngopharyngoscopy (mirror and/or fiberoptic and/or direct procedure) within 42 days prior to registration;

3.1.3.3 Chest CT scan, or PET/CT scan within 42 calendar days prior to registration to rule out metastatic disease;

3.1.3.4 Contrast enhanced CT scan or MRI or PET/CT scan of the tumor site and neck nodes within 42 calendar days prior to registration;

3.1.3.5 EKG and ECHO or MUGA scan within 84 calendar days prior to registration;

- 3.1.4 Zubrod Performance Status 0-1 within 14 calendar days prior to registration;
- 3.1.5 Age \geq 18;
- 3.1.6 CBC/differential obtained within 14 calendar days prior to registration, with adequate bone marrow function defined as follows:
 - 3.1.6.1 Absolute neutrophil count (ANC) \geq 1,500 cells/mm³;
 - 3.1.6.2 Platelets \geq 100,000 cells/mm³;
 - 3.1.6.3 Hemoglobin \geq 8.0 g/dl (Note: The use of transfusion or other intervention to achieve Hgb \geq 8.0 g/dl is acceptable.);
- 3.1.7 Adequate renal and hepatic function within 14 calendar days prior to registration, defined as follows:
 - 3.1.7.1 Serum creatinine < 1.5 mg/dl or creatinine clearance (CC) \geq 50 ml/min within 14 calendar days prior to registration, determined by 24-hour collection or estimated by Cockcroft-Gault formula:
 - CCr male = [(140 – age) x (wt in kg)]
[(Serum Cr mg/dl) x (72)]
 - CCr female = 0.85 x (CrCl male)
 - 3.1.7.2 Total bilirubin < 2 x the institutional ULN;
 - 3.1.7.3 AST or ALT \leq 3 x the institutional ULN;
- 3.1.8 Magnesium, calcium, glucose, potassium, and sodium within 14 calendar days prior to registration, with the following required parameters:
 - 3.1.8.1 Magnesium: > 0.9 mg/dl or < 3 mg/dl;
 - 3.1.8.2 Calcium: > 7 mg/dl or < 12.5 mg/dl;
 - 3.1.8.3 Glucose: > 40 mg/dl or < 250 mg/dl;
 - 3.1.8.4 Potassium: > 3 mmol/L or < 6 mmol/L;
 - 3.1.8.5 Sodium: > 130 mmol/L or < 155 mmol/L.
- 3.1.9 Negative serum pregnancy test within 14 calendar days prior to registration for women of childbearing potential;
- 3.1.10 Women of childbearing potential and men who are sexually active must practice adequate contraception during treatment and for at least 60 calendar days following treatment.
- 3.1.11 Patients must be deemed able to comply with the treatment plan and follow-up schedule.
- 3.1.12 Patients must provide study specific informed consent prior to study entry, including, for oropharyngeal cancer patients, consent for mandatory submission of tissue for required, central p16 review.

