- _____(Y) 1. Does the patient have pathologically (histologically or cytologically) proven diagnosis (from primary lesion and/or lymph nodes) of squamous cell carcinoma of the oropharynx, hypopharynx, or larynx? (**Note:** Patients with oral cavity, nasopharynx, sinuses and salivary gland primary tumors are excluded.)
- _____(Y/N) 2. Does this patient have oropharynx primary? If yes, the patient must agree to consent for mandatory submission of tissue required for central review.
- _____(Y) 3. Does the patient have selected stage III or IV disease: any anatomic site T2 N2-3 M0, T3-4 any N M0; p16 negative oropharynx cancer with T1 N2b, N2c, or N3; or hypopharynx T1-2 any N+?
- _____(Y) 4. Was a history and physical examination done within 28 calendar days prior to registration, including assessment of patient's weight?
- _____(Y) 5. Was the patient examined by a Medical Oncologist and a Radiation Oncologist within 28 calendar days prior to registration?
- _____(Y) 6. Was the patient examined by an ENT or Head and Neck Surgeon (including laryngopharyngoscopy) within 42 days prior to registration?
- _____(Y) 7. Was a Chest CT scan or PET/CT done within 42 calendar days prior to registration ?
- _____(Y) 8. Was a contrast enhanced CT scan or MRI or PET/CT scan of the tumor site and neck nodes done within 42 calendar days prior to registration?
- _____(N) 9. Does the patient have distant metastases?
- _____(Y) 10. Was an EKG and ECHO or MUGA scan done within 84 calendar days prior to registration?
- _____(Y) 11. Was the Zubrod Performance Status 0-1 within 14 calendar days prior to registration?
- _____(Y) 12. Is the patient \geq 18 years of age?
- _____(Y) 13. Does the patient have adequate bone marrow, hepatic and renal function as specified in Section 3.1?
- _____(Y) 14. Were magnesium, calcium, glucose, potassium and sodium done within 14 calendar days prior to registration with results within the parameters required in Section 3.1?
- _____(Y/NA) 15. For women of child bearing potential, was a serum pregnancy test completed within 14 calendar days prior to registration?
- _____(Y) If yes, was the pregnancy test negative?
- _____(Y/NA) 16. If the patient is a woman of child bearing potential or a sexually active male, is the patient willing to use effective contraception during treatment and for at least 60 calendar days following the last study treatment?
- _____(Y) 17. Will the patient be compliant with treatment plan and follow-up schedule?

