3.2 Conditions for Patient Ineligibility (9/27/16)

- 3.2.1 Patients with T1 any N or with T2 N1 are ineligible except for specific oropharynx or hypopharynx patients as described in Section 3.1.3;
- 3.2.2 Patients with simultaneous primaries or bilateral tumors;
- 3.2.3 Gross total excision (e.g., by tonsillectomy) of the primary tumor; however, partial removal of the tumor to alleviate an impending airway obstruction does not make the patient ineligible.
- 3.2.4 Prior invasive malignancy (except non-melanomatous skin cancer) unless disease free for a minimum of 3 years; noninvasive cancers (for example, carcinoma in situ of the breast, oral cavity, or cervix are all permissible) are permitted even if diagnosed and treated < 3 years ago;
- 3.2.5 Prior systemic chemotherapy for the study cancer; note that prior chemotherapy for a different cancer is allowable;
- 3.2.6 Prior radiotherapy to the region of the study cancer that would result in overlap of radiation therapy fields;
- 3.2.7 Primary site of tumor of oral cavity, nasopharynx, sinuses, or salivary glands;
- 3.2.8 Initial surgical treatment, excluding diagnostic biopsy of the primary site or nodal sampling of neck disease; radical or modified neck dissection is not permitted.
- 3.2.9 Prior allergic reaction to the study drugs;
- 3.2.10 Prior therapy that specifically and directly targets the EGFR/HER2 pathway;
- 3.2.11 Patients who have current active hepatic or biliary disease (with exception of patients with Gilbert's syndrome, asymptomatic gallstones, or stable chronic liver disease per investigator assessment);
- 3.2.12 Pregnant women or women of childbearing potential and men who are sexually active and not willing or able to use medically acceptable forms of contraception; this exclusion is necessary because the treatment involved in this study may be significantly teratogenic.
- 3.2.13 Severe, active co-morbidity, defined as follows:

- 3.2.13.1 Uncontrolled cardiac disease, such as uncontrolled hypertension or unstable angina;
- 3.2.13.2 Transmural myocardial infarction within the last 6 months;
- 3.2.13.3 History of congestive heart failure and/or history of left ventricular ejection fraction < 50%;
- 3.2.13.4 Acute bacterial or fungal infection requiring intravenous antibiotics at the time of registration;

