- 3.2.13.5 Chronic Obstructive Pulmonary Disease exacerbation or other respiratory illness requiring hospitalization or precluding study therapy within 30 calendar days prior to registration;
- 3.2.13.6 Hepatic insufficiency resulting in clinical jaundice and/or coagulation defects; note, however, that laboratory tests for liver function and coagulation parameters are not required for entry into this protocol.
- 3.2.13.7 Acquired Immune Deficiency Syndrome (AIDS) based upon current CDC definition; note, however, that HIV testing is not required for entry into this protocol. The need to exclude patients with AIDS from this protocol is necessary because the treatments involved in this protocol may be significantly immunosuppressive. Protocol-specific requirements may also exclude immuno-compromised patients.

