7.2.2 Lapatinib/Placebo: (1/16/14)

Note: See Section 7.2.2.1 for lapatinib/placebo feeding tube administration. See Section 7.6.2 for lapatinib/placebo dose modifications.

Week 1: Starting 7 calendar days prior to radiation, patients will take 6 lapatinib/placebo tablets (1500 mg) once daily, 7 days a week, by mouth or by feeding tube on an empty stomach (either 1 hour before or 1 hour after meals). Lapatinib/placebo tablets are **not** to be crushed.

Weeks 2-7: Concurrent with radiation and cisplatin, patients will take 6 lapatinib/placebo tablets (1500 mg) once daily, 7 days a week, by mouth or by feeding tube on an empty stomach (either 1 hour before or 1 hour after meals). Lapatinib/placebo tablets are **not** to be crushed.

After Concurrent Treatment (Maintenance): After completion of radiation, patients will continue lapatinib/placebo 6 tablets (1500 mg) once daily, 7 days a week, by mouth or by feeding tube on an empty stomach (either 1 hour before or 1 hour after meals) for 3 months.

Patient Diary: Patients will be asked to document daily lapatinib/placebo on a pill diary during concurrent treatment and maintenance, which will be collected by the institution as source documentation. Institutions will submit the DP form to RTOG at the end of concurrent treatment and every month during maintenance treatment (see Sections 11.2.3 and 12.1).

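### As worded, the transaminase entry criterion (3.1.7.3) can be met on AST alone, so entry ALT has no numeric limit although the on-treatment liver rules in 7.7.4 act on ALT

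*Combined protocol and SAP*

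**What the plan says.** Section 3.1.7 asks for adequate renal and hepatic function within 14 calendar days before registration. Its hepatic part has two lines: 3.1.7.2, "Total bilirubin < 2 x the institutional ULN", and 3.1.7.3, "AST or ALT \leq 3 x the institutional ULN". Step 1 checklist item 13 asks "Does the patient have adequate bone marrow, hepatic and renal function as specified in Section 3.1" and adds no number. Appendix I lists bilirubin and AST/ALT before registration, with a time window but no limit.

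Two exclusions touch the liver.

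- **3.2.11**, repeated as checklist item 28, makes active hepatic or biliary disease disqualifying. It exempts Gilbert's syndrome, "asymptomatic gallstones, or stable chronic liver disease per investigator assessment".
- **3.2.13.6** excludes hepatic insufficiency that shows as jaundice and/or coagulation defects. It then notes that "laboratory tests for liver function and coagulation parameters are not required for entry into this protocol".

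During treatment, the enzyme thresholds in 7.7.4 are set on ALT, and none is set on AST.

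- **7.7.4.1** stops drug permanently at ALT > 3 x ULN with total bilirubin > 2.0 x ULN.
- **7.7.4.2** holds drug for 14 days at ALT > 8 x ULN, at ALT > 5 x ULN lasting more than 14 days, or at ALT > 3 x ULN with signs of hepatitis or hypersensitivity.
- **7.7.4.3** lets drug continue at ALT between 3 and 5 x ULN only if bilirubin is ≤ 2 x ULN, there are no such signs and weekly checks are possible. Drug stops if that level lasts more than 28 days.

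Section 11.2.5 schedules bilirubin and AST/ALT 4 weeks after study drug starts.

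**The concern.** The protocol itself warns of hepatobiliary events with lapatinib (7.4.6.2), and it controls that risk on treatment through ALT. The entry screen should therefore limit ALT. As worded it limits only whichever enzyme happens to qualify. If AST qualifies, ALT may be at any level, or may not have been measured at all if a site takes AST/ALT to mean either one.

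Two things are at stake. The first is the safety of a patient who starts 1500 mg daily with an ALT that would prompt action if it appeared later. The second is whether all sites apply the criterion in the same way.

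**Working it through.** The plan gives no figure to reproduce. The check sets the entry rule beside the on-treatment rules. All values are multiples of ULN.

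**1. Is there another ALT limit at entry?** Section 3.1.7.2 limits bilirubin only. Checklist item 13 refers back to Section 3.1. Section 3.2.11 and item 28 are judgments without a value. Section 3.2.13.6 covers jaundice and coagulation defects. Appendix I gives timing. None of them caps ALT.

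**2. What does each wording admit?**

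- As written: the lower of AST and ALT is ≤ 3.
- ALT limit: ALT ≤ 3.
- Both limited: the higher of AST and ALT is ≤ 3.

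Illustrative cases, each with bilirubin 1 (below the entry limit of 2):

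| Case | AST | ALT | As written | ALT limit | Both limited | ALT against 7.7.4 levels |
|---|---|---|---|---|---|---|
| A | 2.5 | 9 | met (2.5 ≤ 3) | not met (9 > 3) | not met | above 8 |
| B | 2.5 | 4 | met (2.5 ≤ 3) | not met (4 > 3) | not met | between 3 and 5 |
| C | 2.5 | 3.0 | met | met (3.0 ≤ 3) | met | none exceeded |

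Cases A and B meet 3.1.7 as written. Either replacement wording excludes them and keeps case C. The highest admissible ALT becomes 3, which exceeds none of the 7.7.4 levels (> 3, > 5, > 8).

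**3. How discordant must the enzymes be?** With AST at its limit of 3, the ratio of ALT to AST must exceed:

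- 3/3 = 1 to pass the > 3 level;
- 5/3 = 1.67 to pass the > 5 level;
- 8/3 = 2.67 to pass the > 8 level.

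Case B therefore needs much less discordance than case A and is the more plausible of the two.

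**4. Which 7.7.4 rule cannot be reached on entry labs?** Section 7.7.4.1 needs bilirubin > 2.0, while entry needs bilirubin < 2. Its combined condition cannot be met by the qualifying tests.

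**5. How soon would the schedule show the ALT again?** The next scheduled test is 28 days after the first dose, and no pre-dose repeat is scheduled. The qualifying test may be up to 14 days before registration, and treatment may start up to 14 days after randomization (Sections 6.0 and 7.0). For a larynx or hypopharynx patient randomized on the day of registration, the gap between scheduled tests is at most 14 + 14 + 28 = 56 days. For oropharynx patients the wait for the p16 result adds to this.

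**6. Does the surrounding wording settle the meaning of the conjunction?** It points both ways. Section 3.1.7.1, in the same list, uses it for a true alternative: serum creatinine or creatinine clearance. Section 3.1.8.1 uses it loosely: "Magnesium: > 0.9 mg/dl or < 3 mg/dl" would admit any value if taken literally, so both bounds must be meant.

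**The case against.** The strongest reply is that no site would enrol such a patient. Section 3.2.11 makes active hepatic disease disqualifying, item 28 asks about it separately, and the registration questions ask whether the investigator considers the patient eligible. An investigator facing an ALT of 9 x ULN would have to judge it either not active disease or stable chronic disease. This carries weight: the exclusion would often catch case A. It is weaker for case B, because it sets no value and stable chronic liver disease is expressly exempt.

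A second reply is that both enzymes were plainly intended, given the drafting habit in 3.1.8, and that eligibility questions can go to the data managers (Section 3.0). Nothing in the documents shows a site accepting AST alone. The intention is probably as described, but 3.1.7.1 stops the text from proving it. Section 3.1.8 has the same looseness and could be tidied separately.

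A third reply is that the change comes late. Section 13.5 projects the end of accrual around March 2017, and Section 7.9 carries a date of 3/22/17. This stands, and it limits how many patients could benefit.

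A reader might go further and infer that a patient with ALT > 8 x ULN at entry already breaches 7.7.4.2, so that drug must be held for 14 days from the outset. The documents do not support that. Section 7.7.4 falls under 7.7, which manages adverse events of study drug, and 7.7.4.2 applies to what a patient experiences. The dose-modification table in 7.6.2 is limited in the same way, to lapatinib-related events. Nothing directs sites to apply either rule to a pre-dose value.

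**Conclusion.** The point holds as a mismatch between thresholds. As worded, 3.1.7.3 can be met on AST alone, entry ALT has no numeric limit, and the backstop is a clinical judgment with an exemption for stable chronic liver disease. A patient could start study drug with an ALT above levels at which 7.7.4 acts later, and the schedule would not recheck it until 4 weeks into dosing.

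The conclusion rests on the literal wording, which was probably not intended. The documents do not say how often the two enzymes disagree in this way; it is assumed to be uncommon. No mandatory hold at entry is claimed, and there is no effect on the PFS comparison, its power or its alpha. The severity is minor: a patient-safety wording correction.

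**What to change.** Change 3.1.7.3 to require ALT ≤ 3 x the institutional ULN. That is the minimum needed, because 7.7.4 sets no AST threshold. If both enzymes were intended, require AST and ALT each ≤ 3 x the institutional ULN. Keep the 14-day window in either case.

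In the note to 3.2.13.6, delete the reference to liver function. It conflicts with 3.1.7 and Appendix I, which presumably govern.

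The cost is a few words. AST/ALT already appears before registration in Appendix I, and item 13 already points to Section 3.1, so the checklist needs no change. A site that had measured only AST would need to add ALT, which 7.7.4 presupposes anyway. A few patients with ALT > 3 x and AST ≤ 3 x ULN would be screened out. The two-enzyme version would also screen out patients with raised AST alone, whom the 7.7.4 rationale does not reach. ALT can still change between the qualifying test and the first dose. With accrual near its end, the clarification may matter more for wording carried into a later trial than for patients still to be enrolled here.
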